**3 \* Describe the duration of an individual participant's participation in the study:**

Approximately 6 months

Sub Study: Approximately 2 hours.

**4 \* Describe the amount of time it will take to complete the entire study:**

Approximately 4 years

Sub Study:

Approximately 1 year.

**5 \* Describe any additional participant requirements:**

n/a

## Sample Size and Data Analysis

**If you uploaded a separate research protocol document in the 'Research Protocol' page, cite the applicable section and page numbers from that document in the answer boxes below.**

**1 \* Provide the rationale and sample size calculations for the proposed target population:**

With a total of 300 participants and an estimated 20% attrition, we will have 60 participants per cell in the factorial design. This will provide a total of 120 participants per main effect condition (Drug or Psychosocial Intervention). Meta analyses of bupropion vs. placebo in the general population estimate the effect as an increase in abstinence from 10% with placebo to 25% with bupropion. The effect for PSF compared to SOC without any drug intervention is estimated to be an increase from 7% to 20%. Using a logistic regression model with alpha equal to .05 (two tailed) we will have greater than 80% power to detect these main effects. We will assess whether the combination of PSF and bupropion will have a simple additive effect on smoking abstinence (no interaction) or synergistic effect on smoking cessation (interaction). We will have 80% power to detect a 10% increase in relative abstinence when PSF is compared to SOC without bupropion to PSF compared to SOC with bupropion. Power was calculated using the PASS software. (Version 13, Logistic Regression Procedure.)

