**1 \* Describe the purpose, specific aims, or objectives of this research. State the hypothesis to be tested:**

Primary Aim 1: Compare bupropion therapy to placebo on rates of 7-day point prevalence abstinence (PPA) at 36 weeks in smokers with HIV/AIDS. We hypothesize that rates of smoking abstinence at week 36 will be higher in those treated with bupropion compared to placebo.

Primary Aim 2: Compare Positively Smoke Free to low intensity, brief counseling on rates of 7-day PPA at 36 weeks in smokers with HIV/AIDS. We hypothesize that rates of smoking abstinence at week 36 will be higher in those treated with Positively Smoke Free compared to brief counseling.

Primary Aim 3: Compare Positively Smoke Free + bupropion to the other two study conditions outlined above on rates of 7-day PPA in smokers with HIV/AIDS at 36 weeks. We hypothesize the effect of Positively Smoke Free with bupropion therapy is greater than the effect of Positively Smoke Free or bupropion therapy alone.

Secondary Aim: Estimate the organizational costs of implementing Positively Smoke Free, bupropion or both. All cost estimates will be appropriately time-discounted and inflation-adjusted. The planned assessment will yield rigorously obtained approximations of total implementation costs at a new site of care.

Exploratory Aim: Explore whether the effect of PSF compared to brief counseling with bupropion is greater than the effect of PSF without bupropion.

Given the critical need for information about the up-front expenses required to implement smoking cessation services in Kenya, we plan to conduct an implementation costs assessment to provide rigorously obtained approximations of total implementation costs of each intervention tested in this trial.

Sub Study:

AIM 1: Develop, culturally adapt and update the PSF intervention in the main study to include educational material about the cancer risk associated with tobacco and alcohol use.

AIM 2: Preliminarily determine the extent the updated PSF syllabus changes awareness of the link between alcohol and tobacco use and cancer.

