Female participants who have the potential to become pregnant will have a pregnancy test during the evaluation phase and approximately monthly during the study (while taking study medication). They will be asked to use acceptable method of contraception during the medication phase of the study (week 1-12). Participants will sign a contraception consent to confirm their agreement (In the baseline packet). Condoms will also be provided at research appointments.

Baseline Interview:

Participants will also complete a series of assessment questionnaires (baseline interview). Vital signs will also be recorded. Only those continuing to meet full inclusion criteria and do not meet exclusion criteria will proceed to randomization and remain in the study. The list of assessments to be completed are located in the study schedule in the Additional Documents section.

Randomization

Study participants who are deemed eligible for the study will complete baseline testing and will then be randomized 1:1:1:1 to four study conditions: (1) Bupropion + PSF; (2) Bupropion + SOC; (3) Placebo + PSF; (4) Placebo + SOC. Participants will be randomly assigned to one of the four conditions using permuted blocks which will randomly vary in size. The research pharmacy will be notified of the drug randomization (Bupropion or placebo). All raters, investigators, and other staff will be blind to treatment assignment except for the dispensing pharmacist. Separate emergency unblinding envelopes for each participant will be kept in a locked cabinet at the dispensing pharmacy in the case of a medical emergency. All participants who are randomized will be taught the correct use of the study medication, and assisted in setting a quit date with the instruction to quit on approximately Day 8 (beginning of Week 2) following one week of medication.

Medication Intervention:

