**Please note:**

We have increased the total N from 445 to 650, an increase of about 200. This was done for 2 reasons:

1. We previously added a sub study in a prior modification and did not increase the N at that time because enrollment numbers were lower. We have since then consented several individuals to the sub study and we are close to reaching our current N.

2. In the beginning, most individuals we consented for the main smoking study were eligible, however, after consenting approximately 200 individuals, we are having more difficulty consenting individuals who meet eligibility after screening. We may Consent 5 individuals and only 1 is eligible.

We are still keeping the main study at 300 individuals, therefore we are not updating the total N in the consent form. We may need to consent 400 people in order to have 300 eligible.

**2 \* Provide the plan for data analysis. Include in the description the types of comparisons that are planned (e.g., comparison of means, comparison of proportions, regressions, analysis of variance, etc.), which is the primary comparison/analysis, and how the analyses proposed will relate to the primary purposes of the study:**

**Primary Aims:** We will use generalized linear mixed models (SAS, 9.3: Proc GLIMMIX) using a contrast for each post baseline time point to assess the main effects of bupropion vs. placebo (Drug) and PSF vs. SOC (Beh) on smoking cessation. In addition we will assess the interaction of Drug\*Beh and any covariates that were identified above. The test of the hypotheses will be the test of whether the coefficients for the main effects and the interaction are significantly different from 0 based on the likelihood ratio test. If the interaction is significant, we will run additional analyses to explore the simple main effects and will interpret those as opposed to the main effects.

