*** Full Title: Optimizing smoking cessation interventions for PLWH in Nairobi, Kenya**

STATISTICAL ANALYSIS PLAN

Power Calculations: With a total of 300 participants and an estimated 20% attrition, we expect 60 participants per cell in the factorial design. This will provide a total of 120 participants per main effect condition (Drug or Psychosocial Intervention). All power analyses were conducted with a two tailed alpha of .05 and powerset to .80. With the expected sample and the anticipated retention rate, the study's 2 main effects((1) bupropion vs. placebo; (2) PSF versus SOC) are each powered to detect a Cohen's h of from .28 to .36 (small effect)98. In addition, we will be able to determine if there is a significant additive effect (i.e. whether the combination of bupropion and PSF is significantly better than either treatment alone). For this comparison we have sufficient power to detect an effect size of $h = .39 - .49$ (small to medium effect). The evaluation of the exploratory interaction Aim is a possible but not necessary benefit of a factorial design that could determine whether the combination of the two treatments provides more than a simple additive effect. The interaction effect is powered to detect a Cohen's d of .9 (large effect)98. Power was calculated using the PASS software. (Version 13, Logistic Regression Procedure.)

Overview of Analytic Methods: The primary study analyses will adopt an intent-to-treat strategy. Data will be screened for errors using frequency and contingency tables and univariate and bivariate plots before formal analysis. These plots and summaries will allow us to be cognizant of data distribution characteristics before building regression models. To assess indication of self-selection bias, we will compare the demographic characteristics of the participants that agreed to participate in the study to those who were approached, but were not interested in participating.

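### The scale on which the combination is called additive is never stated, and the protocol's logistic interaction test does not test additivity in quit rates

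*Protocol*

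**What the plan says.** Protocol, Sample Size and Data Analysis, item 1, gives the expected effects as abstinence percentages: 10% to 25% for bupropion against placebo, and 7% to 20% for PSF against SOC without drug. It bases main-effect power on logistic regression ("Using a logistic regression model with alpha equal to .05 (two tailed) we will have greater than 80% power to detect these main effects"). It then says the trial will assess whether the combination "will have a simple additive effect on smoking abstinence (no interaction) or synergistic effect on smoking cessation (interaction"). No scale is attached to the word additive.

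Item 2 of the same section (Primary Aims) uses Proc GLIMMIX with Drug, Beh and Drug*Beh. The test is of "whether the coefficients for the main effects and the interaction are significantly different from 0 based on the likelihood ratio test". No link is named there; logit is inferred from item 1. If the interaction is significant, simple effects are interpreted in place of main effects.

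The exploratory aim in Justification, Objective, & Research Design, item 1, is to "Explore whether the effect of PSF compared to brief counseling with bupropion is greater than the effect of PSF without bupropion".

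The SAP is different. Its Power Calculations section calls the interaction exploratory and says it "could determine whether the combination of the two treatments provides more than a simple additive effect". Its Primary Aims section fits logistic models with main effects only, and compares the combination with each single treatment through a three-condition indicator. Neither that section nor Exploratory Analyses specifies a Drug*Beh model. Neither document plans an interaction estimate on the risk scale.

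**The concern.** A zero interaction coefficient in a logistic model means that the odds ratios multiply. It does not mean that the extra quitters from the two treatments add up. With low baseline quit rates and odds ratios near 3, these are clearly different hypotheses. A combination can yield more quitters than the sum of its parts and still have an interaction odds ratio below 1.

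The exploratory aim asks whether PSF does more when given with bupropion. The direction of the answer can depend on the scale, and the plan does not say which scale it means. The Lay Summary names policymakers as an audience and the protocol plans implementation costs for each intervention. Both uses call for quitters gained per person treated, which is the risk scale.

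**Working it through.** **Inputs.** Allocation: "will then be randomized 1:1:1:1 to four study conditions". Size: "With a total of 300 participants and an estimated 20% attrition, we will have 60 participants per cell in the factorial design", so 120 per main-effect level. Two-sided alpha is 0.05. PSF effect without drug: 7% to 20%. Bupropion effect: 10% to 25%; the background text also says bupropion doubles the odds. The documents give no four-cell rates, so the bupropion + SOC rate is **an assumption**, and I carry five values.

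**The plan's own figure.** Main-effect power is Φ{[|d| − 1.96·√(2p̄(1−p̄)/n)] / √(p₁(1−p₁)/n + p₂(1−p₂)/n)} with n = 120.
- 10% vs 25%: (0.15 − 0.0961)/0.0481 = 1.12, power 87%.
- 7% vs 20%: (0.13 − 0.0865)/0.0433 = 1.005, power 84%.

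A Wald test of the log odds ratio gives 84% and 81%. The claim of more than 80% is reproduced.

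**The two nulls for the combined arm.** Let p00 = 0.07 (placebo + SOC), p01 = 0.20 (placebo + PSF), p10 = bupropion + SOC and p11 = the combination.
- Additive in quit rates: p11 = p10 + p01 − p00 = p10 + 0.13.
- Zero logistic interaction: odds11 = odds10 × odds01/odds00 = odds10 × (0.25/0.0753) = odds10 × 3.32.

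Worked case, p10 = 22%: the additive value is 35.0%. The logistic null has odds 0.2821 × 3.3214 = 0.937, or 48.4%. The gap is 13.4 points. At 35%, the interaction OR is 0.5385/0.937 = 0.575.

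**Chance of each result at exact additivity, 60 per cell.** SE of the log interaction OR = √Σ 1/(60·p(1−p)). For p10 = 22% this is √(0.2560 + 0.1042 + 0.0971 + 0.0733) = 0.728. ln 0.575 = −0.554, so the expected z is −0.76. P(negative estimate) = Φ(0.76) = 78%. P(significantly negative) = Φ(−1.96 + 0.76) = 11.5%.

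**Precision of the risk-scale estimate.** The 95% CI half-width for the difference in differences is 1.96·√Σ p(1−p)/60. For p10 = 22% this is 1.96·√0.0104 = 20.0 points.

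| Bupropion + SOC (assumed) | Additive p11 | Logistic null p11 | Gap (points) | Interaction OR at additivity | P(estimate negative) | P(significantly negative), Wald | CI half-width (points) |
|---|---|---|---|---|---|---|---|
| 13.1% (odds doubled from 7%) | 26.1% | 33.3% | 7.2 | 0.71 | 67% | 7% | 18.4 |
| 17.5% (7% × 2.5) | 30.5% | 41.3% | 10.8 | 0.62 | 74% | 9% | 19.3 |
| 18.4% (OR 3 applied to 7%) | 31.4% | 42.9% | 11.4 | 0.61 | 75% | 10% | 19.5 |
| 22% (7% + 15 points) | 35.0% | 48.4% | 13.4 | 0.58 | 78% | 11.5% | 20.0 |
| 25% (taken as stated) | 38.0% | 52.5% | 14.5 | 0.55 | 79% | 13% | 20.4 |

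A simulated likelihood ratio test (4,000 runs per scenario, last four rows) gave 11% to 14% significantly negative and 74% to 80% with a negative estimate.

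**Reversal of sign.** Take p10 = 22% and a true combined rate of 40%. PSF then adds 18 points with bupropion against 13 without, yet the interaction OR is 0.71. The logistic test is significantly negative in about 7% to 8% of such trials and significantly positive in under 1%.

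**The case against.** Three arguments on the other side have force.

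First, a reader might infer that a combination additive or better in quit rates would be reported as sub-additive. The documents do not support that. The protocol decides by a significance test, not by the sign of the estimate, and it offers only additive or synergistic as labels. At exact additivity roughly 86% to 93% of trials would be non-significant and would receive the additive label, which happens to be the right word. The *or better* part is also bounded: it holds only up to the multiplicative-odds rate, 33% to 53% across the scenarios. This objection stands. What it leaves is that the additive label would rest on failing to reject a different hypothesis, in a test with an SE of about 0.7 to 0.8 on the log scale. Real gains in quit rates beyond additivity would receive the same label.

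Second, additive may simply mean no product term on the model's own scale, since the sentence follows one about logistic regression. That reading is possible. It means the fault is an unstated scale, not a test proven to be wrong. But the effects beside it are quit percentages, and the two readings differ by 7 to 15 points in the combined arm.

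Third, a reader might infer that the SAP's conclusion about the combination is compromised. It is not. The SAP's three-condition comparison does not use the interaction coefficient, and the SAP calls the interaction exploratory.

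It is also fair that a risk-scale interval of about ±18 to 20 points will seldom settle the question. The interval would at least show this, which a bare no-interaction label does not.

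**Conclusion.** The point holds as a minor one. The protocol equates no interaction with additivity in abstinence, but its test has multiplicative odds as the null. Neither document states the scale, and the SAP keeps the question without specifying a model for it.

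Under the assumed cell rates, the two nulls are about 7 to 15 points apart. An exactly additive combination has a true interaction OR of about 0.55 to 0.71. Its estimate would be negative in roughly 67% to 80% of trials, but significantly so in only about 7% to 14%. The likely harm is therefore a non-significant test read as additivity in quit rates, together with a point estimate whose sign may be opposite to the quit-rate answer.

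This rests on a logit link inferred from the sample-size section, on 60 analysed per cell, and on an assumed 13% to 25% for bupropion + SOC. The direction of the gap is the same at all five values.

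**What to change.** In the SAP's Exploratory Analyses, for the exploratory aim:
- Add a week-36 logistic model with Drug, Beh, Drug*Beh and the planned covariates.
- From it, report the four standardised abstinence risks and their difference in differences with a 95% CI.
- Beside it, report the ratio of odds ratios with its CI, labelled as departure from multiplicative odds.
- Name the scale wherever additive or synergistic is used, and state that a non-significant logit interaction is not evidence of additivity.

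Bring the wording of the protocol's sample-size and Primary Aims text into line.

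The cost is a few lines of text and one added exploratory model, since the SAP does not currently fit one with Drug*Beh. The risk-scale interval will be wide, about ±18 to 20 points at 60 per cell, and should be presented as such. Design, sample size, data collection and the SAP's primary comparisons do not change.

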values in the various study scales. If necessary, we will conduct a sensitivity analysis to investigate how estimates/results change over a range of several plausible assumptions regarding the missing mechanism together with multiple imputations to most accurately capture existent random variability. Multiple Comparisons: We will use the sequential Bonferroni-type procedure for dependent hypothesis tests⁹⁹ to control the false discovery rate (the expected (or on average) proportion of falsely rejected hypotheses) at 5%. Primary Aims: We will use separate logistic regression models (SAS, 9.3: Proc Logistic) at each post baseline time point to assess the main effects of bupropion vs. placebo (Drug) and PSF vs. SOC (Beh) on smoking cessation. In addition, we will assess any covariates that were identified above. The test of the hypotheses will be the test of whether the coefficients for the main effects are significantly different from 0 based on the likelihood ratio test. To assess if the combination of bupropion and PSF is significantly more effective than either of the treatments alone, we will create an indicator variable for these 3 conditions with the combined treatment as the reference. The analysis will proceed as described above.

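### The protocol's 80% power for a 10% PSF-by-bupropion interaction is not attainable at 60 per cell: the power is about 5–20% with the effect tested on its own scale, and the SAP contradicts it.

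*Protocol*

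**What the plan says.** Protocol, Sample Size and Data Analysis, item 1: "With a total of 300 participants and an estimated 20% attrition, we will have 60 participants per cell in the factorial design". The planned abstinence rates are 10% against 25% for placebo and bupropion, and 7% against 20% for SOC and PSF when no drug is given. Alpha is .05 two-sided and the model is logistic regression. On the interaction it states: "We will have 80% power to detect a 10% increase in relative abstinence when PSF is compared to SOC without bupropion", to be set against PSF compared with SOC in the presence of bupropion. It adds that the trial will assess whether the two treatments are additive or synergistic.

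Protocol, item 2 of the same section, Primary Aims: the Drug*Beh interaction is tested by likelihood ratio test alongside the main effects. If it is significant, the team will "explore the simple main effects and will interpret those as opposed to the main effects".

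Protocol, Justification, Objective, & Research Design, item 1, lists the same question as exploratory: "Exploratory Aim: Explore whether the effect of PSF compared to brief counseling with bupropion is greater than the effect of PSF without bupropion".

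SAP, Power Calculations, with the same 300 participants, attrition, cell size, alpha and software: "The evaluation of the exploratory interaction Aim is a possible but not necessary benefit of a factorial design", and "The interaction effect is powered to detect a Cohen's d of .9 (large effect".

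SAP, Primary Aims, names only the main effects and a three-condition comparison of the combination with each treatment alone: "The test of the hypotheses will be the test of whether the coefficients for the main effects are significantly different from 0".

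**The concern.** An interaction contrast draws on four cells of 60, so its variance is about four times that of a main effect estimated from two groups of 120. A design that has a little over 80% power for main effects of 13 to 15 points cannot also have 80% power for a 10-point interaction. It is further still from 80% for a 1.1-fold one.

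The consequence is in interpretation. The protocol offers the test as a way to separate additivity from synergy, and its result decides which effects are interpreted. A reader who believes the 80% figure would take a non-significant interaction as evidence of additivity and keep the main-effect reading on that basis. With power near 5–20% for the stated effect, non-significance says almost nothing about it.

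**Working it through.** **Inputs from the documents.** 300 × 0.8 / 4 = 60 per cell; two-sided alpha .05; placebo+SOC 7%; placebo+PSF 20%.

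**Assumption.** The bupropion+SOC rate, b, is not given. I use 7% to 25%.

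**The plan's own main-effect claim.** Two-proportion power at 120 per arm is 86.9% for 10% vs 25% and 84.3% for 7% vs 20%. Both exceed 80%, as stated, so the method reproduces the part of the claim that can be reproduced.

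**Interaction formulas.** Sums run over the four cells, n = 60. Power = Φ(|δ|/SE − 1.96) + Φ(−|δ|/SE − 1.96).

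- Risk difference: δ = (p11 − b) − (0.20 − 0.07); SE = √Σ p(1−p)/n.
- Log odds ratio: δ = log of the ratio of odds ratios; SE = √Σ 1/[n p(1−p)].
- Log risk ratio: δ = log of the ratio of risk ratios; SE = √Σ (1−p)/(n p).

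**Example, b = 10%.** For a 10-point interaction, p11 = 10% + 13% + 10% = 33%.

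- Risk difference: Σ p(1−p) = 0.0651 + 0.1600 + 0.0900 + 0.2211 = 0.5362; SE = √(0.5362/60) = 0.0945; δ/SE = 1.058; power 18.5%.
- Logit: ratio of odds ratios 1.335, log 0.289, SE 0.788, δ/SE = 0.366; power 6.6%.
- For a ratio of risk ratios of 1.1, p11 = 1.1 × 0.10 × 0.20/0.07 = 31.4%; log 1.1 = 0.0953; SE 0.689; power 5.2%.

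**Across the range of b, 60 per cell:**

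| b | 10 points, risk difference | 10 points, logit Wald (interaction OR) | 10 points, simulated likelihood ratio test | Ratio of RRs 1.1, log-RR scale | Same 1.1 cells, logit Wald |
|---|---|---|---|---|---|
| 7% | 19.5% | 9.9% (1.71) | 11.2% | 5.2% | 5.2% |
| 10% | 18.5% | 6.6% (1.33) | – | 5.2% | 5.9% |
| 13.5% | 17.6% | 5.2% (1.11) | 6.1% | 5.3% | 7.5% |
| 20% | 16.4% | 5.2% (0.91) | 6.1% | 5.3% | 16% |
| 25% | 15.9% | 5.7% (0.83) | 6.4% | 5.3% | 37% |

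The simulation used 20,000 runs. At b = 20% and above, a positive 10-point interaction is an odds ratio below 1, so without a stated scale even the direction is undefined.

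**Other readings tried.**

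- All 75 per cell analysed at the same rates: 19–23%, 5–11% and about 5% for the risk-difference, logit and log-RR tests.
- One-sided alpha, b from 10% to 25%: 25–28% for 10 points as a risk difference, about 10% for the 1.1 ratio.
- A simple two-arm 10-point contrast: 22–39% at 60 per arm and 39–67% at 120 per arm; the best case, 7% vs 17% one-sided, is 77%.

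**What 60 per cell can detect at 80% power.**

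- Risk difference: 27–29 points.
- Interaction OR: 7.5–10.3 with the SE held at the 10-point cells, or 9.0–10.4 with the SE evaluated at the alternative. The latter imply a difference-in-differences of about 52–56 points, so these are separate tests and not one effect on two scales.
- Cohen's h: 2.80 × √(4/60) = 0.72; the 10-point interaction is h = 0.09–0.23.

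Eighty per cent power for 10 points needs (1.96 + 0.84)² × Σ p(1−p) / 0.10² = 393–520 evaluable per cell.

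**The SAP's d = .9.** Read as a log-odds d (an assumed conversion), OR = exp(0.9π/√3) = 5.1, with 51–58% power in the logit test. Read as h, .9 is larger than the detectable 0.72. Neither reading returns 80%.

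**The case against.** The decisive rate is assumed, and the protocol does not define its 10%. That is true, but the conclusion holds across the whole range of b. The upper end of 5–20% comes from a risk-difference test that the plan does not specify; in the planned logistic test a 10-point interaction has roughly 5–11%.

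The most favourable case is a 1.1 ratio of risk ratios with b at 20–25%. It reaches 16–37% in the logistic test (44% with 75 per cell), and it needs 63–79% abstinence in the combined arm. The same cells tested as a risk difference do pass 80%, but only because they imply an absolute interaction of 30 to 41 points, which is not a 10% effect on the scale being tested.

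The SAP already limits the harm: it calls the interaction exploratory and detectable only if large. Neither document says that a non-significant test will be reported as proof of additivity. This is why the remedy is confined to text. The protocol sentence is still current, however, and the two documents disagree. Because the scale of d is not stated, the size of that disagreement cannot be given.

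One further point stands. The 84.3% for PSF uses 7% and 20% as marginal rates, as the protocol does, although it describes them as rates without drug. If they are the placebo cells and effects add on the risk-difference scale, PSF main-effect power is about 77% at b = 13.5% and 68% at b = 25%; under logit additivity it stays above 80%. The 84.3% therefore confirms the protocol's calculation and does not establish main-effect power for every set of cell rates.

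**Conclusion.** The stated 80% power is wrong as written. At 60 per cell and two-sided .05, with placebo cells of 7% and 20% and bupropion+SOC assumed between 7% and 25%, power is 16–20% for a 10-point interaction on the risk-difference scale and 5–10% by logit Wald (6–11% by simulated likelihood ratio test). It is about 5% for a 1.1 ratio of risk ratios on its own scale. No reading tried reaches 80% in the planned logistic test. The sentence also conflicts with the SAP's figure from the same inputs, and that figure itself needs rechecking. The protocol's Primary Aims text is out of line with its own exploratory aim and with the SAP. This should be fixed; it does not call the sample size of 300 into question.

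**What to change.** 1. Delete the 80%/10% sentence from the protocol's sample size rationale.
2. In both documents, state the interaction scale, all four assumed cell rates, and the interaction detectable with 80% power at 60 per cell computed from them. Recheck d = .9 in the same step and replace it with a measure suited to a binary outcome. The detectable sizes above are for orientation only.
3. In the protocol's Primary Aims analysis, move Drug*Beh to exploratory status, in line with the protocol's Exploratory Aim and the SAP. Report it as an estimate with a 95% confidence interval, and state that a non-significant test will not be read as evidence of additivity.

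The cost is text only: sample size, randomisation and primary endpoint do not change. The stated interaction power becomes less favourable, and rates for the two bupropion cells must be assumed and justified.
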